3.7.7. Columbia Suicide Severity Rating Scale (C-SSRS)

Columbia Suicide Severity Rating Scale items of suicidal behavior and suicidal ideation will be summarized at baseline and post-baseline by prior ALKS 5461 exposure and overall for the Safety Population. The proportion of subjects who meet the criterion for each of these categories will be summarized as described in Table 10. Each item will be presented separately within each category (suicidal behavior, suicidal ideation, self-injurious behavior without suicidal intent). Any suicide attempt (aborted, interrupted, and actual) will also be summarized as a category. Data will be presented for baseline, any post-baseline (i.e. on treatment), and any post-discontinuation values.

Any behaviors experienced will be listed with a brief narrative. Any completed suicides will be presented with full narrative.

Table 10: C-SSRS Summary Categories for Analysis

Category	C-SSRS item response is "YES"	
Suicidal ideation	1) Wish to be dead	
	2) Non-specific active suicidal thoughts	
	3) Active suicidal ideation with any methods (not plan) without intent to act	
	4) Active suicidal ideation with some intent to act, without specific plan	
	5) Active suicidal ideation with specific plan and intent	
Suicidal behavior	6) Preparatory acts or behavior	
	7) Aborted attempt	
	8) Interrupted attempt	
	9) Actual attempt	
	10) Completed suicide	
Suicidal behavior or ideation	Including 10 items above	
Self-injurious behavior without suicidal intent	Purely for other reasons / without any intention of killing yourself	

Summary of treatment emergent suicide-related events based on the C-SSRS during treatment period will be presented by prior ALKS 5461 exposure and overall for the Safety Population. The degree and type of treatment emergent suicide-related events will be summarized in a table as defined in Table 11. Post-discontinuation assessments will not be included in this analysis.

This analysis population consists of safety population with non-missing baseline and at least 1 post-baseline assessment during treatment period. The percentage will be calculated for the treatment emergent suicide-related event summary. The numerator is defined as the number of subjects with a non-missing baseline and a post-baseline C-SSRS assessment meeting the treatment emergent suicide-related numerator criteria defined in Table 11, and the denominator is defined as the number of subjects with a non-missing baseline and at least 1 post-baseline C-SSRS assessment meeting the treatment emergent suicide-related denominator criteria defined in Table 11 during treatment period.

Table 11: Treatment Emergent Suicide-related Events for Analysis

Treatment Emergent Suicide- related Events	Denominator Criteria	Numerator Criteria
Increase in Suicidal Ideation from Baseline	Baseline suicidal ideation ("No" to all ideation items 1- 5, or "Yes" to any ideation item ≤4 and "No" to item 5)	Baseline suicidal ideation ("No" to all ideation items 1-5, or "Yes" to any ideation item ≤4 and "No" to item 5)
		Post-baseline (increase in suicidal ideation severity from baseline at any post-baseline visit)
Emergence of Serious Suicidal Ideation	Baseline suicidal ideation ("No" to all ideation items 1-5, or "Yes" to any ideation item≤3 and "No" to items 4 and 5)	Baseline suicidal ideation ("No" to all ideation items 1-5, or "Yes" to any ideation item ≤3 and "No" to items 4 and 5) Post-baseline ("Yes" to ideation item 4 or 5 at any post-baseline visit)
Emergence of Serious Suicidal Ideation in Subjects with no Suicidal Ideation at Baseline	Baseline ideation ("No" to all ideation items 1-5)	Baseline ideation ("No" to all ideation items 1-5) Post-baseline ("Yes" to ideation item 4 or 5 at any post-baseline visit)
Decrease in Suicidal Ideation from Baseline	Baseline ideation ("Yes" to any ideation items 1-5)	Baseline ideation ("Yes" to any ideation items 1-5) Post-baseline (decrease in suicidal
		ideation severity at any post- baseline visit compared to severity at baseline)
Emergence of Suicidal Behavior in Subjects with no Suicidal Behavior	Baseline behavior ("No" to all behavior items 6-10)	Baseline behavior ("No" to all behavior items 6-10)
at Baseline		Post-baseline behavior ("Yes" to any behavior items 6-10 at any post-baseline visit)

3.7.8. Clinical Opiate Withdrawal Scale (COWS) Scores

COWS will be administered only at EOT and post-discontinuation visits, so COWS will be analyzed for Post-discontinuation Safety Population. For Post-discontinuation Safety Population, baseline COWS is defined as EOT COWS assessment. Adequate COWS baseline is defined as EOT COWS assessment being performed within (\leq) 2 days of last dose of study drug.

Subjects will be included in the COWS analysis if they have an adequate EOT COWS and at least 1 post-EOT COWS in the post-discontinuation safety period. COWS will be summarized by:

- Analysis of all post-EOT COWS assessments
- Analysis of post-EOT COWS assessments that occurred from >2 to 16 days post last dose of study drug

Subjects with inadequate EOT COWS, i.e. EOT COWS assessment was performed more than (>) 2 days of last dose, will be included in a supportive listing.

Although opioid withdrawal might not be expected in individuals with less than 4 weeks of drug exposure, COWS will be presented in all subjects with adequate EOT COWS, and then COWS will be subset by duration of study drug exposure. Three COWS analyses will be presented for the subjects with adequate EOT COWS by the 3 exposure subgroups (any exposure, ≥4 weeks exposure, <4 weeks exposure):

- Total COWS scores (baseline and change from baseline, and days between last dose and assessment date) will be summarized by visit (baseline, post-discontinuation visits)
- Subject count and incidence will be provided by visit for each of the COWS total score categories indicated below:

No withdrawal: total score 0-4

Mild withdrawal: total score 5-12

Moderate withdrawal: total score 13-24

Moderately severe withdrawal: total score 25-36

- Severe withdrawal: total score >36

COWS category shift summary from baseline to post-baseline: the numerator is the
number of subjects in each post-discontinuation COWS category with non-missing
baseline COWS. If there are more than one post-discontinuation COWS, i.e. a subject
with an unscheduled visit, the highest value will be used. The denominator is the
number of subjects in each baseline COWS category.

Data listing of COWS scores at each visit will be provided. Narratives will be provided for any clinically meaningful COWS shifts.

4. INTERIM ANALYSES

No interim analysis is planned.

5. CHANGES IN CONDUCT OR PLANNED ANALYSES FROM THE PROTOCOL

N/A.

6. DEFINITIONS AND CONVENTIONS FOR HANDLING OF THE DATA

Dataset specifications will be provided in a separate document.

6.1. Analysis Visit Windows

Every attempt must be made to provide complete data. In cases where complete data cannot be collected, the principles to assign the analysis visits for inclusion in summary tables described in this section will be followed for data handling and analyses.

Early termination visits for efficacy measurements will be mapped to the next scheduled visit. For example, a subject who terminates shortly after Day 29 (e.g., has assessments at baseline through Day 29, and Day 365 or early termination) would have assessments at early termination mapped to the next scheduled visit for each assessment. In this example, the MADRS and CGI-S from the early termination visit would be mapped to Day 43; and the HAM-A results would be mapped to Day 57. For other visits other than early termination / Day 365, the visit number indicated on the CRF (i.e., CRF visit) will be used as the analysis visit.

Early termination visits for safety measurements will not be mapped to any scheduled post-baseline visit, but will be used as the last assessment during treatment period.

Measurements collected from unscheduled visits will not be included in the by-visit summary tables or mean change analyses but will be included in the analysis of outlier and PCS values and in the subject listings.

6.2. Efficacy Data Handling

MADRS-10 is the sum of the 10 items from the MADRS. HAM-A total score is the sum of 14 items from the HAM-A. If only one of the items of the MADRS, or HAM-A for a given visit is missing, then the total score will be calculated using (sum of non-missing items) × (total number of items) / (number of non-missing items). If more than one of the items are missing, the total score will be set to missing. The MADRS-6 and HAM-A subscale scores will be set to missing if any item is missing.

6.3. Handling of Partial Dates of Prior and Concomitant Medications

Partial start dates of prior and concomitant medications will be assumed to be the earliest possible date consistent with the partial date. Partial stop dates of prior and concomitant medications will be assumed to be the latest possible date consistent with the partial date. In the case of completely missing stop date, medication will be assumed to be ongoing.

7. GENERAL STATISTICAL METHODOLOGY

7.1. Statistical Conventions

In general, summary statistics (n, mean, standard deviation [SD], median, minimum and maximum for continuous variables, and number and percentage of subjects in each category for categorical variables) will be provided by study group. All summary tables will be based on observed data, and missing values will not be imputed unless otherwise indicated. Measurements collected from unscheduled visits or repeated assessments will not be included in the by-visit summary or mean change tables or figures, but will be included in the analyses for the outlier / PCS post-baseline values, and subject listings. Source data for the summary tables and statistical analyses will be presented as subject data listings.

7.2. Reporting Precision

Summary statistics will be presented to the degree of precision in Table 12, unless otherwise specified.

Table 12: Degree of Precision

Statistics	Degree of Precision
Mean, Median, Quartiles, Confidence	One more than the raw data, up to 3 decimal places.
limit boundaries	
Standard deviation, Standard error	One more than the mean, up to 3 decimal places.
Minimum, Maximum	The same as the raw data.
p-value	Rounded to 3 decimal places and therefore presented
	as 0.xxx; p-values smaller than 0.001 as '<0.001'; p-
	values greater than 0.999 as '>0.999'.
Percentage	One decimal place. A percentage of 100% will be
	reported as 100%. Percentages of zero will be
	reported as 0.

Fractional numeric values will be presented with a zero to the left of the decimal point (for example, 0.12–0.30).

For weight, height, and BMI, one decimal place will be used for summary statistics.

8. PROGRAMMING SPECIFICATIONS

Programming specifications will be provided in a separate document.

9. MOCK TABLES, LISTINGS AND FIGURES (TLFS)

Mock-up tables, listings, and figures will be provided in a separate document.

APPENDIX 1. AESI – ABUSE POTENTIAL

Preferred Term	Adhoc SOC
Accidental overdose	AP_abuse behavior
Drug abuser	AP_abuse behavior
Drug diversion	AP_abuse behavior
Drug level above therapeutic	AP_abuse behavior
Drug level increased	AP_abuse behavior
Drug screen	AP_abuse behavior
Drug screen positive	AP_abuse behavior
Intentional overdose	AP_abuse behavior
Intentional product misuse	AP_abuse behavior
Intentional product use issue	AP_abuse behavior
Maternal use of illicit drugs	AP_abuse behavior
Needle track marks	AP_abuse behavior
Neonatal complications of substance abuse	AP_abuse behavior
Overdose	AP_abuse behavior
Prescription drug used without a prescription	AP_abuse behavior
Prescription form tampering	AP_abuse behavior
Product tampering	AP_abuse behavior
Substance abuse	AP_abuse behavior
Substance abuser	AP_abuse behavior
Substance use	AP_abuse behavior
Substance-induced mood disorder	AP_abuse behavior
Substance-induced psychotic disorder	AP_abuse behavior
Toxicity to various agents	AP_abuse behavior
Acute psychosis	AP_non-specific
Aggression	AP_non-specific
Cognitive disorder	AP_non-specific
Confusional state	AP_non-specific
Delirium	AP_non-specific
Delusional disorder, unspecified type	AP_non-specific
Depersonalisation/derealisation disorder	AP_non-specific
Disorientation	AP_non-specific
Dissociation	AP_non-specific
Disturbance in attention	AP_non-specific
Disturbance in social behaviour	AP_non-specific
Dizziness	AP_non-specific
Dopamine dysregulation syndrome	AP_non-specific
Emotional disorder	AP_non-specific
Flight of ideas	AP_non-specific
Medication overuse headache	AP_non-specific

Preferred Term	Adhoc SOC
Mental impairment	AP_non-specific
Mood altered	AP_non-specific
Mood swings	AP_non-specific
Narcotic bowel syndrome	AP_non-specific
Paranoia	AP_non-specific
Psychotic behaviour	AP_non-specific
Psychotic disorder	AP_non-specific
Sedation	AP_non-specific
Somnolence	AP_non-specific
Stupor	AP_non-specific
Euphoric mood	AP-euphoria related
Feeling abnormal	AP-euphoria related
Feeling drunk	AP-euphoria related
Feeling of relaxation	AP-euphoria related
Hallucination	AP-euphoria related
Hallucination, auditory	AP-euphoria related
Hallucination, gustatory	AP-euphoria related
Hallucination, mixed	AP-euphoria related
Hallucination, olfactory	AP-euphoria related
Hallucination, synaesthetic	AP-euphoria related
Hallucination, tactile	AP-euphoria related
Hallucination, visual	AP-euphoria related
Inappropriate affect	AP-euphoria related
Thinking abnormal	AP-euphoria related

APPENDIX 2. AESI – DEPENDENCE

Preferred Term
Dependence
Drug dependence
Drug dependence, antepartum
Drug dependence, postpartum
Drug tolerance
Drug tolerance decreased
Drug tolerance increased
Substance dependence

APPENDIX 3. AESI – WITHDRAWAL

Drug detoxification Reversal of opiate activity Drug rehabilitation Drug withdrawal convulsions Drug withdrawal headache Drug withdrawal maintenance therapy Drug withdrawal syndrome Drug withdrawal syndrome neonatal
Drug rehabilitation Drug withdrawal convulsions Drug withdrawal headache Drug withdrawal maintenance therapy Drug withdrawal syndrome
Drug withdrawal convulsions Drug withdrawal headache Drug withdrawal maintenance therapy Drug withdrawal syndrome
Drug withdrawal headache Drug withdrawal maintenance therapy Drug withdrawal syndrome
Drug withdrawal maintenance therapy Drug withdrawal syndrome
Drug withdrawal syndrome
Drug withdrawal syndrome neonatal
Rebound effect
Steroid withdrawal syndrome
Withdrawal arrhythmia
Withdrawal syndrome
Anhedonia
Depressed mood
Depression
Dysphoria
Feeling of despair
Morose
Negative thoughts
Persistent depressive disorder
Dyssomnia
Headache
Insomnia
Obsessive thoughts
Poor quality sleep
Syncope
Terminal insomnia
Agitation
Irritability
Anxiety
Chills
Hyperhidrosis
Nausea
Nervousness
Pain
Tremor
Vomiting
Abdominal pain
Arthralgia

Preferred Term	
Diarrhoea	
Mydriasis	
Piloerection	
Restlessness	
Rhinorrhoea	
Tachycardia	
Yawning	

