 13. Have initiated or had dose adjustment to hormone replacement therapy (including testosterone) or an oral contraceptive within 30 days of screening
 14. Have used inducers or moderate to strong inhibitors of cytochrome P450 (CYP) 3A4 (prescription medications, over-the-counter medications [OTC], or dietary supplements) within 30 days prior to screening (see [Appendix A](#) for examples of prohibited CYP3A4 modulators)
 15. Have received electroconvulsive therapy treatment within the last 2 years, or received more than 1 course of electroconvulsive treatment during their lifetime
 16. Pose a current suicide risk, as evidenced by any of the following:
 - a. it is the opinion of the investigator that the subject may be at risk for suicide
 - b. the subject responds “Yes” to Question # 4 (“Active Suicidal Ideation with Some Intent to Act, Without Specific Plan”) or Question # 5 (“Active Suicidal Ideation with Specific Plan and Intent”) on the Baseline Columbia Suicide Severity Rating Scale (C-SSRS), if the most recent episode occurred within the past 12 months
 - c. the subject has attempted suicide within the past 2 years

17. Have a QT interval >450 msec for men and >470 msec for women, assessed in a relaxed state, as corrected by the Fridericia formula (QTcF) observed at Visit 1 or Visit 2
 18. Have an aspartate aminotransferase or alanine transaminase measurement of >2 times the upper limit of normal at Visit 1.
 19. Have current evidence of or history of any of the following:
 - a. compromised respiratory function (eg, chronic obstructive pulmonary disease, respiratory depression, signs or symptoms of hypoxia at screening)
 - b. thyroid pathology (unless stabilized and euthyroid for >3 months at the time of screening)
 - c. seizure disorder (excluding febrile seizures)
 - d. hepatitis or human immunodeficiency virus (HIV) infection
 - e. myasthenia gravis
 - f. any contraindicated medical condition as per the approved labeling for buprenorphine
 20. Have current evidence of, or a history in the past 12 months of, alcohol or substance abuse or dependence (excluding nicotine) per DSM-IV-TR criteria as assessed by the MINI
 21. Have a positive breath alcohol test at screening
 22. Have a history of intolerance, allergy or hypersensitivity to BUP or opioid antagonists (eg, naltrexone, naloxone)

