
Resting Pulse Rate: _____ beats/minute Measured after patient is sitting or lying for one minute
 
0 pulse rate 80 or below 1 pulse rate 81-100 2 pulse rate 101-120 4 pulse rate greater than 120
	
GI Upset: over last ½ hour
 
0 no GI symptoms 1 stomach cramps 2 nausea or loose stool 3 vomiting or diarrhea 5 Multiple episodes of diarrhea or vomiting

Sweating: over past ½ hour not accounted for by room temperature or patient activity.
 
0 no report of chills or flushing 1 subjective report of chills or flushing 2 flushed or observable moistness on face 3 beads of sweat on brow or face 4 sweat streaming off face
	
Tremor observation of outstretched hands
 
0 No tremor 1 tremor can be felt, but not observed 2 slight tremor observable 4 gross tremor or muscle twitching

Restlessness Observation during assessment
 
0 able to sit still 1 reports difficulty sitting still, but is able to do so 3 frequent shifting or extraneous movements of legs/arms 5 Unable to sit still for more than a few seconds
	
Yawning Observation during assessment
 
0 no yawning 1 yawning once or twice during assessment 2 yawning three or more times during assessment 4 yawning several times/minute

Pupil size
 
0 pupils pinned or normal size for room light 1 pupils possibly larger than normal for room light 2 pupils moderately dilated 5 pupils so dilated that only the rim of the iris is visible
	
Anxiety or Irritability
 
0 none 1 patient reports increasing irritability or anxiousness 2 patient obviously irritable anxious 4 patient so irritable or anxious that participation in the assessment is difficult

Bone or Joint aches If patient was having pain previously, only the additional component attributed to opiates withdrawal is scored
 
0 not present 1 mild diffuse discomfort 2 patient reports severe diffuse aching of joints/ muscles 4 patient is rubbing joints or muscles and is unable to sit still because of discomfort
	
Gooseflesh skin
 
0 skin is smooth 3 piloerection of skin can be felt or hairs standing up on arms 5 prominent piloerection

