
Runny nose or tearing Not accounted for by cold symptoms or allergies
 
0 not present 1 nasal stuffiness or unusually moist eyes 2 nose running or tearing 4 nose constantly running or tears streaming down cheeks
	
Total Score _____
 
The total score is the sum of all 11 items
 
Initials of person completing Assessment: _____

Score: 5-12 = mild; 13-24 = moderate; 25-36 = moderately severe; more than 36 = severe withdrawal

**APPENDIX H. STRUCTURED INTERVIEW GUIDE FOR THE
MONTGOMERY-ÅSBERG DEPRESSION RATING
SCALE (SIGMA) - SAMPLE**

STRUCTURED INTERVIEW GUIDE FOR THE MONTGOMERY AND ASBERG DEPRESSION RATING SCALE (SIGMA)

Janet B.W. Williams, D.S.W. and [name].

INTERVIEWER: The questions in bold for each item should be asked exactly as written. Often these questions will elicit enough information about the severity and frequency of a symptom for you to rate the item with confidence. Follow-up questions are provided, however, for use when further exploration or additional clarification of symptoms is necessary. The specified questions should be asked until you have enough information to rate the item confidently. In some cases, you may also have to add your own follow-up questions to obtain necessary information. Note that questions in parentheses are optional, for use, for example if information is unknown.

NOTES:

Time period. The ratings should be based on the patient's condition in the past week.

Change from baseline. In general, a symptom is rated as present only when it reflects a change from before the depression began (baseline). The interviewer must identify a 2-month period of non-depressed functioning and use this as a reference point. In some cases, such as when the patient has dysthymia the referent should be to the last time the person felt all right (i.e. not depressed or high) for at least a few weeks. When a clear baseline cannot be established because of chronic depressive symptoms, current symptoms should be rated as observed over the past 7 days.

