APPENDIX 7. AESI – RESPIRATORY DEPRESSION

Preferred Term
Acute respiratory failure
Apnoea
Apnoeic attack
Bradypnoea
Breath holding
Breath sounds abnormal
Breath sounds absent
Central-alveolar hypoventilation
Hypopnoea
Hypoventilation
Hypoventilation neonatal
Infantile apnoea
Lung hypoinflation
Neonatal respiratory arrest
Neonatal respiratory depression
Neonatal respiratory failure
Postoperative respiratory failure
Respiratory arrest
Respiratory depression
Respiratory depth decreased
Respiratory failure
Respiratory paralysis
Respiratory rate decreased

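### The withdrawal AESI list in SAP Appendix 3 has no terms for several symptoms that the trial's own COWS form scores, so the withdrawal AESI table can undercount

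*SAP*

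**What the plan says.** SAP 3.7.3 summarises adverse events of special interest by preferred term. For withdrawal it takes post-discontinuation events with onset more than 2 and up to 16 days after the last dose, which it describes as the period in which physiological opioid withdrawal presents. It shows them for any exposure, at least 4 weeks and less than 4 weeks. Each AESI group has its own listing, and narratives are promised for clinically meaningful events within the group. The terms are those under "APPENDIX 3. AESI – WITHDRAWAL".

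The trial also measures withdrawal with COWS (protocol Appendix G). Its 11 items include "Bone or Joint aches", with an anchor reading "2 patient reports severe diffuse aching of joints/ muscles", and "Runny nose or tearing". The lowest positive anchor of the sweating item is "subjective report of chills or flushing". The top anchor of the tremor item covers muscle twitching as well as gross tremor.

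SAP 3.7.8 analyses COWS totals, severity categories and shifts separately. SAP 3.7.2 tabulates all post-discontinuation events by system organ class and preferred term.

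**The concern.** Physical dependence is an obvious long-term safety question for a product containing buprenorphine. The AESI table is the only adverse-event summary that applies the withdrawal window and the exposure split. If its list is narrower than the trial's own measure of withdrawal, a subject whose complaints after stopping are muscle aches and watery eyes can be missing from it. The two planned views of withdrawal could then differ because of how the list was built and not because of what subjects experienced.

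**Working it through.** No sample size or error rate is involved; the check is a side-by-side comparison. The inputs are the Appendix 3 terms (46 distinct once extraction repeats are removed) and the 11 COWS items with their anchors.

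**Items with an uncovered part**

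| COWS item | Terms in Appendix 3 | Scored on COWS, no term in Appendix 3 |
|---|---|---|
| Bone or joint aches | Arthralgia, Pain | muscle ache, bone ache |
| Runny nose or tearing | Rhinorrhoea | tearing, nasal stuffiness |
| Sweating | Hyperhidrosis, Chills | flushing |
| Tremor | Tremor | muscle twitching |

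The other 11 − 4 = 7 items (pulse, restlessness, pupil size, GI upset, yawning, anxiety or irritability, gooseflesh) each have a matching term and no comparable gap. The uncovered components number 2 + 2 + 1 + 1 = 6. A text search of the list for muscle, myalg, musculo, bone, lacrim, tear, flush and twitch finds nothing; a search for ache finds only the two headache terms. Nasal congestion is not listed either.

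**Is it an extraction artefact?** The start of Appendix 3 is garbled, but its last block is alphabetical from Abdominal pain to Yawning. Diarrhoea is followed directly by Mydriasis, where terms for flushing, lacrimation, muscle twitching or myalgia would fall. The omission appears real.

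**What the gap can do.** Score severe diffuse muscle aching (2), tearing (2) and visible flushing (2): 2 + 2 + 2 = 6. That lies in the 5–12 band, mild withdrawal in both Appendix G and SAP 3.7.8. The same complaints, reported as adverse events and coded to their specific terms, give 0 entries in the withdrawal AESI table.

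**Does COWS fill the gap?** Protocol Table 3 puts clinic visits on post-treatment days 1, 7, 14 and 28 and phone contacts on days 2–6, 10 and 21. Nominally, the scheduled contacts inside the window are days 3, 4, 5, 6, 7, 10 and 14. Only 2 of these 7 (days 7 and 14) include COWS; the other 5 are phone contacts that collect adverse events. Sweating and GI upset are rated over the past half hour, and restlessness, tremor and yawning are observed at the assessment, so a symptom that has resolved can be missed. SAP 3.7.8 also requires an end-of-treatment COWS within 2 days of the last dose and at least one later COWS. Subjects whose end-of-treatment COWS was too late are only listed. The population for post-discontinuation adverse events (SAP 3.2.1) has no such COWS condition.

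**The case against.** The strongest reply is that these symptoms are not lost. COWS is itself a planned withdrawal result with a matching 2-to-16-day analysis, and its total sums all 11 items. The events also appear in the general post-discontinuation tables and AE listings. Aches coded to Pain or Arthralgia are counted, as is anything reported as a withdrawal syndrome. A phone report related to opioid withdrawal prompts an in-clinic COWS. The symptoms named there are only examples, the shift table takes the highest value including unscheduled visits, and clinically meaningful COWS shifts have their own narratives. Nothing in the SAP obliges Appendix 3 to mirror COWS, and the study is descriptive, with no test resting on this table.

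Most of that stands. It rules out the stronger conclusion a reader might draw, that such events never reach any withdrawal result. It does not remove the gap. The call-back depends on someone recognising the complaint as withdrawal-related. The general tables carry neither the withdrawal window nor the exposure split. The AESI listing and narratives depend on membership of the list. Nor does a wish for specificity explain the omission: the list already admits headache, insomnia, nausea, depression and pain, and it takes one half of a COWS item while leaving out the other (rhinorrhoea without tearing, arthralgia without muscle ache). The SAP gives no reason.

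**Conclusion.** The point holds as a limited gap in one table. Six components across 4 of 11 COWS items have no preferred term in Appendix 3, and events coded specifically to them are left out of the withdrawal AESI table, its listing and its AESI narratives. The direction is an undercount. Its size cannot be computed, because the documents give no event frequencies.

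Two assumptions are needed. First, Appendix 3 is the operative selection list; its title says so, although SAP 3.7.3 does not cite it. Second, at least some of these complaints are coded to their own terms and not to Pain or a withdrawal syndrome. That depends on verbatim reports and on MedDRA 19.0, neither of which is available here.

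A reader might extend the argument to "APPENDIX 7. AESI – RESPIRATORY DEPRESSION", which has no hypoxia term, because the protocol excludes New Subjects with "signs or symptoms of hypoxia at screening". The documents do not support that step: this is an eligibility criterion, and it lists hypoxia and respiratory depression as separate examples of compromised respiratory function. Nor do the steroid and neonatal withdrawal terms in Appendix 3 matter, since terms that are never used change no result.

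**What to change.** Before database lock, compare Appendix 3 with protocol Appendix G item by item and add the matching preferred terms, confirmed in MedDRA 19.0. At the least these are myalgia, bone pain and lacrimation increased; flushing or hot flush, muscle twitching and nasal congestion should also be added. If a component is left out on purpose, state the reason in the SAP. Have SAP 3.7.3 cite Appendix 3 explicitly as the selection list.

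The work is a revised search list and no new data. The cost is some background noise, chiefly from nasal congestion and flushing, which are non-specific. Because the table is by preferred term, readers can see those events and discount them.
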